2.2 Study Design

This is a prospective cohort study to be conducted at HPTN study sites located in Chililabombwe, Zambia; Durban, South Africa; Hlabisa, South Africa; Lusaka, Zambia; and Moshi, Tanzania. The study design and visit/procedures schedule are summarized in the Schema and in Appendix I. All procedures are consistent with those specified for implementation in HPTN 035.

Each study site will target enrollment of 240 study participants over the course of a six-month accrual period, according to the following schedule of monthly enrollment targets:

- Study month 1: 20 participants
- Study month 2: 30 participants
- Study month 3: 40 participants
- Study month 4: 50 participants
- Study month 5: 50 participants
- Study month 6: 50 participants

The study follow-up period then will extend for at least six months, and up to a maximum of 12 months, from the end of the accrual period.

It is expected that each study site will be activated to implement HPTN 035 by the end of the six-month follow-up period, however if this is not the case, the follow-up period may be extended for up to another six months, pending activation of HPTN 035. Possible reasons for a delay in activation of HPTN 035 include delays in finalizing the HPTN 035 protocol and implementation plans, delays in manufacturing and packaging the investigational products for HPTN 035, delays in obtaining ethical review and approval of the HPTN 035 protocol, and indication based on performance in this study that additional preparedness work is required prior to transitioning to HPTN 035. On a site-by-site basis, upon activation of HPTN 035, this study will be terminated and participants will be invited to screen for HPTN 035.

As described more fully in Section 3.3, potential study participants will be screened for eligibility and enrolled in the study over the course of up to 30 days, and over the course of at least one Screening Visit and one Enrollment Visit.

Enrolled participants then will complete monthly follow-up assessments throughout the duration of their participation. At each visit, participants will complete an interval medical/menstrual history and undergo pregnancy testing. HIV and sexually transmitted disease (STD) risk reduction counseling messages will be reinforced as needed and condoms and other prevention supplies will be distributed.

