3.5 Participant Retention

Once a participant enrolls in this study, the study site will make every effort to retain her in follow-up to minimize possible bias associated with loss-to-follow-up. It is recommended that participant retention procedures be established at each site such that loss-to-follow-up rates do not exceed the 5-6 percent average annual HIV seroincidence rate expected to be observed in the control groups of HPTN 035. As such, annual retention rates of 95 percent are targeted. Site staff are responsible for developing and implementing local standard operating procedures to achieve this goal. Components of such procedures include:

- Thorough explanation of the study visit schedule and procedural requirements during the informed consent process, and re-emphasis at each study visit.
- Collection of detailed locator information at the study Screening Visit, and active review and updating of this information at each subsequent visit.
- Use of mapping techniques to establish the location of participant residences and other locator venues.
- Use of appropriate and timely visit reminder mechanisms.
- Immediate and multifaceted follow-up on missed visits.
- Mobilization of trained outreach workers or "tracers" to complete in-person contact with participants at their homes and/or other community locations.
- Regular communication with the study community at large to increase awareness of HIV/AIDS and explain the purpose of HIV prevention research and the importance of completing research study visits.

The HPTN CORE will provide the study sites with a participant tracking database to facilitate visit scheduling and timely identification and follow-up on missed visits. The HPTN SDMC will generate weekly reports on the number and percentage of participants completing quarterly follow-up assessments. The Protocol Team as well as the HPTN Study Monitoring Committee will track retention rates closely and work with study sites as needed to take any required action to address below-target retention rates.

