6.2.1 Secondary Endpoints

Consistent with the secondary study objectives, the following will be assessed as secondary endpoints:

- Potential participants screened for the study, and the screening outcome for each screenee.
- Participants enrolled in the study.

- Participants retained in the study until the site-specific study end date.
- Demographic characteristics of women screened for and/or enrolled in the study, including:
 - Age
 - Race/ethnicity
 - Educational level
 - Employment status
 - Income level
- HIV risk behaviors reported by women enrolled in the study, including:
 - Number of sex partners
 - Frequency of vaginal intercourse
 - Frequency of unprotected vaginal intercourse
 - Frequency of anal intercourse
 - Frequency of unprotected anal intercourse
- Prevalent (i.e., at screening/enrollment) and incident (i.e., during follow-up) occurrences of the following:
 - Pelvic exam findings involving deep epithelial disruption
 - Genital ulcer disease
 - Other genital signs and symptoms
 - Bacterial vaginosis
 - Candidiasis
 - Chlamydia infection
 - Gonorrhea infection
 - Syphilis infection
 - Trichomoniasis

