6.3 Accrual, Follow-up, and Sample Size

Each participating study site will target accrual of 240 study participants within the six-month accrual period, with the monthly enrollment targets presented in Section 2.2. Each site also will target retention of 95 percent of enrolled participants annually (or 97.5 percent semi-annually).

As will be described in Section 6.4.2, assessment of the study outcomes related to accrual and retention will not require statistical analysis. However the precision of study estimates of HIV and STD incidence depends on the number of participants enrolled and retained in the study, as well as the "true" seroincidence rate. Shown in Tables 1 and 2 below are the widths of exact 95% confidence intervals around site-specific incidence rates, assuming the accrual schedule presented in Section 2.2 and retention of 97.5 percent of participants semi-annually, with either a sixmonth (Table 1) or twelve-month (Table 2) follow-up period, and an expected 117 and 234 woman-years of follow-up, respectively.

Table 1
95% Exact Confidence Intervals for Infection Rates
Observed in a Six-Month Follow-up Period

Observed in a dix-month i dilow-up i eriod								
No. Infections	Observed	95% Exact						
Observed	Infection Rate	Confidence Interval						
1	1.7%	0.2-6.2%						
2	3.4%	0.9-8.8%						
3	5.1%	1.8-11.2%						
4	6.8%	2.9-13.5%						
5	8.5%	4.0-15.7%						
6	10.3%	5.3-17.9%						

Table 2
95% Exact Confidence Intervals for Infection Rates
Observed in a Twelve-Month Follow-up Period

No. Infections Observed	Observed Infection Rate	95% Exact Confidence Interval
2	1.7%	0.4-4.4%
4	3.4%	1.4-6.7%
6	5.1%	2.6-9.0%
8	6.8%	3.9-11.1%
10	8.5%	5.2-13.2%
12	10.3%	6.5-15.3%

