6.4.2 Secondary Analyses

Corresponding to the secondary study objectives, the following secondary analyses will be performed:

- The study accrual process will be described by tabulating the number and rate of potential participants screened for and enrolled in the study at each site, overall and by month during the accrual period. Each site's actual accrual rates will be compared to the target rates, and reasons for ineligibility for the study will be tabulated.
- The number of enrolled participants retained in the study will be tabulated for each site for the entire site-specific follow-up period as well as for each quarter in the follow-up period. Retention rates also will be calculated. The denominator for these calculations will be the total number of participants enrolled in the study at the site. The numerator will include all participants at the site who complete a scheduled visit during the interval and/or are known to have died during a previous interval. Retention rates for each site will be compared to the annual target of 95 percent.
- The demographic characteristics of persons screened for and/or enrolled in the study at each site will be described. At a minimum, the characteristics listed in Section 6.2 will be tabulated.
- The HIV risk behaviors of persons enrolled in the study at each site will be described. At a minimum, the frequency of each of the outcomes listed in Section 6.2 will be tabulated.
- The baseline prevalence for each of the genital signs and symptoms and infections listed in Section 6.2 will be computed for the enrolled study population at each site, as the total number of endpoints observed among enrollees divided by the number of participants enrolled. Appropriate 95% confidence intervals also will be computed. An incidence rate for each of the genital signs and symptoms and infections listed in Section 6.2 also will be computed for each study site, as the total number of endpoints observed divided by the total number of person-years of follow-up. Confidence intervals will be calculated based on Poisson distribution assumptions.

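### Section 6.4.2 sets retention over 6-12 months against an annual 95% target, so a site losing about 7% a year could be shown as meeting it

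*Supplement*

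**What the plan says.** Section 6.3 sets the target: "Each site also will target retention of 95 percent of enrolled participants annually (or 97.5 percent semi-annually". Section 3.5 gives the reason for it: sites should keep retention such that "loss-to-follow-up rates do not exceed the 5-6 percent average annual HIV seroincidence rate" expected in the HPTN 035 control groups.

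Section 6.4.2 says how retention is reported. The number retained is "tabulated for each site for the entire site-specific follow-up period as well as for each quarter in the follow-up period". On the denominator: "The denominator for these calculations will be the total number of participants enrolled in the study at the site". The numerator is "all participants at the site who complete a scheduled visit during the interval and/or are known to have died during a previous interval". The comparison rule follows: "Retention rates for each site will be compared to the annual target of 95 percent". The matching endpoint in Section 6.2 is "Participants retained in the study until the site-specific study end date".

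On follow-up time, Section 2.2 states: "It is expected that each study site will be activated to implement HPTN 035 by the end of the six-month follow-up period". It allows up to six further months if activation of HPTN 035 is delayed. Section 6.1 gives each woman between six and 12 scheduled monthly assessments.

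**The concern.** A proportion retained means something only with a time attached. Section 6.4.2 takes proportions accumulated over less than a year and sets them against a one-year figure. It does not scale them, name a time point or use person-time, although the incidence analyses in Sections 6.4.1 and 6.4.2 do use woman-years or person-years. Less time at risk means fewer losses, so the comparison favors the site.

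The study exists to show whether sites are ready for HPTN 035, which Section 1.2 says needs high retention over 12-24 months. A site whose annual loss exceeds the 5-6% in Section 3.5 could be described as on target. Sites that close at different times would also be set against one fixed figure over different lengths of follow-up.

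**Working it through.** **Inputs.** Enrollment of 20, 30, 40, 50, 50 and 50 in study months 1-6, total 240 per site (Section 2.2); expected close at study month 12 (Section 2.2); at most 12 monthly assessments per woman (Section 6.1); visit window of two weeks either side (Section 4.4); targets of 95% annual and 97.5% semi-annual (Section 6.3).

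**Assumptions that are not in the documents.** Enrollment is even within each month. Loss is permanent and at a constant rate. The whole-period rate is the share retained to the site end date, following the endpoint in Section 6.2. Deaths are ignored.

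**1. The plan's own figures.** √0.95 = 0.9747 and 0.975² = 0.9506, so 97.5% is the six-month equivalent of 95% a year. The expected woman-years also reproduce: 240 × 0.5 × 0.975 = 117 and 240 × 1 × 0.975 = 234.

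**2. Follow-up at the expected close.** Using mid-month enrollment, (20×11.5 + 30×10.5 + 40×9.5 + 50×8.5 + 50×7.5 + 50×6.5) / 240 = 2050/240 = 8.54 months. All 240 women reach month 6. None passes 12 full months. About 10 (half of the first month's 20) come inside the early side of the month-12 window.

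**3. Like-for-like benchmark.** For a site at 95% a year, expected whole-period retention is the average of 0.95^(t/12) over the 240 women. By enrollment month this is 0.9520, 0.9561, 0.9602, 0.9643, 0.9685 and 0.9726. Weighted by 20, 30, 40, 50, 50 and 50, it comes to 231.4/240 = 96.4%. At exactly six months per woman it is 97.5%.

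**4. Break-even.** Solving for the annual retention that gives 95% over the whole period yields 93.0%, a loss of 7.0% a year. If each woman contributes only six months, which is the basis of the 117 woman-years, the break-even is 0.95² = 90.25%, a loss of 9.75% a year.

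**5. Chance of at least 95% (228 of 240), binomial.**

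| True annual loss | Expected whole-period retention | Chance at expected close | Chance, six months each | Chance, full year each |
|---|---|---|---|---|
| 5% | 96.4% | 91% | 99% | 58% |
| 6% | 95.7% | 76% | 97% | 31% |
| 7% | 95.0% | 57% | 91% | 14% |
| 8% | 94.2% | 37% | 81% | 5% |

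**6. Extension.** With a close at study month 15 and the 12-month cap, the benchmark is 95.4% and the break-even loss is 5.4% a year. With a close at month 18 and the cap, every woman has 12 months, the benchmark is 95.0% and the break-even is 5%.

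**7. Late quarters.** At the expected close only the first 20 + 30 + 40 = 90 women have reached the month-9 date: 90/240 = 37.5%. Counting the early side of the window adds half of month 4's 50: 115/240 = 47.9%. Even if any monthly visit in that quarter counts, those who have reached month 7 number 190/240 = 79.2%, or 215/240 = 89.6% with the window. For the month-12 visit it is about 10/240 = 4.2%. Over all enrolled, every site would fall below 95% in these quarters however good its retention.

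**The case against.** The strongest reply is that the plan already holds the right benchmark. Section 6.3 states the target on both time scales, so the annual target in Section 6.4.2 can be read as shorthand for a like-for-like comparison, with details left to a separate analysis plan. This does not settle it: Section 6.4.2 defines numerator, denominator and intervals, then names only the annual figure. Section 6.3 also says the accrual and retention outcomes need no statistical analysis, so annualization cannot be presumed.

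Several other points stand.

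- **The effect is modest.** The gap between 96.4% and 95.0% is about 3.4 women in 240 (231.4 against 228). The binomial standard error at 95% of 240 is √(0.95 × 0.05/240), also about 1.4 points.
- **No formal rule turns on it.** Retention is a descriptive secondary outcome. Weekly reports and the Study Monitoring Committee follow it separately (Section 3.5), and no section makes transition to HPTN 035 depend on this comparison. Section 2.2 does list performance in this study as one of four possible reasons for delay.
- **Quarterly rates should not be compounded.** A reader might infer that 95% at month 3 means 0.95⁴ = 81.5% a year, or that 95% at month 6 means 90.25%. The numerator is attendance in an interval, and Sections 4.4 and 4.5 provide for women who return after a missed visit. Those conversions hold only if every absence is permanent.
- **Extended sites are not penalized.** A reader might infer that sites kept longer face a stricter standard. With the 12-assessment cap in Section 6.1, a full extension gives exactly the intended 95%.

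**Conclusion.** The point holds in a limited form. As written, Section 6.4.2 sets retention over an average of about 8.5 months against a one-year target. On the whole-period rate, a site losing about 7% a year could be shown as meeting it, with about a 57% chance against 14% over a full year. The matching benchmark is about 96.4% for the whole period, or the protocol's own 97.5% at month 6.

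It would go too far to say that such a site would be reported as meeting the target: the chance is a little better than even at 7% and falls to 37% at 8%. Nor is every rate lenient. The leniency applies to the whole-period, month-3 and month-6 rates. At the expected close, third- and fourth-quarter rates over all enrolled err in the opposite direction, and the leniency vanishes if all women complete 12 months. The sizes rest on constant permanent loss, even enrollment within months and a close at study month 12.

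**What to change.** Replace the comparison sentence in Section 6.4.2 with text such as:

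*Retention at the month-6 visit, which all enrolled women reach, will be compared with 97.5 percent. Where follow-up is extended, retention at month 12 among women due that visit will be compared with 95 percent. The whole-period rate will be reported as annualized loss (or as a Kaplan-Meier estimate) and compared with 5 percent a year. Other quarterly rates will be reported descriptively among women due the visit.*

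The change to women due the visit is needed: a time-scaled benchmark applied to quarterly rates over all enrolled would still fail in late quarters. The denominator sentence in the same section needs matching wording.

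The cost is a few lines of text and no new data, since enrollment and visit dates are already collected. The downside is that some sites will look slightly less favorable.

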2.1.2 Secondary Objectives

The secondary objectives of this study are to:

- Develop and describe the accrual process and estimate rates of accrual into a standardized HIV-related research study among women targeted for inclusion in HPTN 035.
- Estimate rates of retention in a standardized HIV-related research study among women targeted for inclusion in HPTN 035.
- Describe the demographic characteristics and HIV risk behaviors of women targeted for inclusion in HPTN 035.
- Estimate prevalence and incidence rates of the following among women targeted for inclusion in HPTN 035:
 - Pelvic exam findings involving deep epithelial disruption
 - Genital ulcer disease
 - Other genital signs and symptoms
 - Bacterial vaginosis (BV)
 - Candidiasis
 - Chlamydia infection
 - Gonorrhea infection
 - Syphilis infection
 - Trichomoniasis

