3.2 Exclusion Criteria

Women who meet any of the following criteria will be excluded from this study:

- History of adverse reaction to latex.
- History of non-therapeutic injection drug use in the 12 months prior to screening.
- Had vaginal intercourse more than an average of two times per day in the two weeks prior to screening.
- At screening:
 - Plans to travel away from the study site for more than three consecutive months in the next 12 months.
 - Plans to relocate away from the study site in the next 12 months.
 - Plans to become pregnant in the next 12 months.
- At screening or enrollment:
 - Enrolled in any other study of a vaginally-applied product.
 - Pregnant.
- At enrollment, is within 42 days of last pregnancy outcome.
- At enrollment, has a clinically apparent pelvic exam finding involving deep epithelial disruption.

Note: Otherwise eligible participants with pelvic exam finding(s) involving deep epithelial disruption may be enrolled after the finding has resolved. If resolution is documented within 30 days after obtaining informed consent for screening, screening procedures need not be repeated.

• At enrollment, diagnosed with a current STD and/or other reproductive tract infection requiring treatment according to WHO guidelines.

Note: Participants will undergo laboratory testing for chlamydia, gonorrhea, and syphilis at their screening visits, and wet mount testing for BV, candidiasis, and trichomoniasis at their enrollment visits; all results will be available at the enrollment visits. Otherwise eligible participants diagnosed at their enrollment visits with infection(s) requiring treatment per WHO guidelines (other than asymptomatic candidiasis) will be offered treatment and may be enrolled after completing treatment and all symptoms have resolved. If treatment is completed and symptoms have resolved within 30 days after obtaining informed consent for screening, screening procedures need not be repeated.

• At enrollment, has any other condition that, in the opinion of the Investigator or designee, would preclude provision of informed consent, make participation in the study unsafe, complicate interpretation of study outcome data, or otherwise interfere with achieving the study objectives.

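### Baseline prevalence in 6.4.2 uses enrollees only, so it understates prevalence among otherwise eligible screened women to the extent that infected women enroll less often

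*Supplement*

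**What the plan says.** The secondary objective in 2.1.2 is to "Estimate prevalence and incidence rates of the following among women targeted for inclusion in HPTN 035", followed by a list of nine genital findings and infections. The Secondary Endpoints list under 6.2 defines the outcome as "Prevalent (i.e., at screening/enrollment) and incident (i.e., during follow-up) occurrences of the following".

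The analysis in 6.4.2 narrows this. Prevalence "will be computed for the enrolled study population at each site", and the formula is "as the total number of endpoints observed among enrollees divided by the number of participants enrolled". The same section describes demographics for women screened and/or enrolled, but plans no prevalence figure for screened women.

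Section 3.2 lists two exclusions that concern the same conditions:
- "At enrollment, diagnosed with a current STD and/or other reproductive tract infection requiring treatment according to WHO guidelines"
- "At enrollment, has a clinically apparent pelvic exam finding involving deep epithelial disruption"

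Neither is permanent. A woman with an infection "will be offered treatment and may be enrolled after completing treatment and all symptoms have resolved", and the infections meant are those "other than asymptomatic candidiasis". Deep epithelial disruption must have resolved. Section 3.3 requires enrollment within 30 days of screening consent; otherwise screening is repeated. The 2003 letter of amendment changes the chlamydia and gonorrhea test methods but not the prevalence analysis, and the 2004 clarification memorandum does not touch it either.

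**The concern.** Enrollment depends on the outcome being estimated. An infected woman has to come back, finish treatment and be free of symptoms before she can enter the denominator; an uninfected woman faces none of these steps. If she does not get through them, she leaves both numerator and denominator, and no other planned prevalence figure captures her.

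Section 6.4.2 also does not say which result is used for a woman who was infected, treated and then enrolled, or for a woman screened twice. Two analysts could follow the text and report different figures.

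The study exists to prepare sites for HPTN 035. A low estimate would mislead planning on how much infection a site will meet among the women it screens. The confidence interval would not warn of this, since it reflects sampling error only.

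**Working it through.** The documents state no prevalence figure and no precision for one, so there is none to reproduce.

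**Who can be lost.** Section 3.3 places the Enrollment Visit about 7 to 14 days after screening, when results are expected. Counting from screening consent, 30 − 14 = 16 to 30 − 7 = 23 days then remain to complete treatment and clear symptoms without a repeat screen.

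**Who can still count as a case.** Chlamydia, gonorrhea and syphilis are tested at the Screening Visit. The pelvic exam and wet mount are done at the Enrollment Visit, before a woman with a finding is enrolled. Under the endpoint definition, a woman treated and then enrolled has a prevalent occurrence and can enter the numerator.

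**Formula.** Let p be prevalence among otherwise eligible screened women, e the probability that an uninfected woman enrolls, and r·e the probability that an infected woman enrolls. If every enrollee's pre-treatment result counts, then

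prevalence among enrollees = p·r·e / (p·r·e + (1 − p)·e) = p·r / (p·r + 1 − p).

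**Inputs.** Both p and r are assumptions; the documents give neither. For p = 20%:
- r = 1: 0.20 / (0.20 + 0.80) = 20.0%
- r = 0.9: 0.18 / (0.18 + 0.80) = 18.4%
- r = 0.75: 0.15 / (0.15 + 0.80) = 15.8%
- r = 0.5: 0.10 / (0.10 + 0.80) = 11.1%

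The same formula over a range of p:

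| Assumed p | r = 1 | r = 0.9 | r = 0.75 | r = 0.5 |
|---|---|---|---|---|
| 10% | 10.0% | 9.1% | 7.7% | 5.3% |
| 20% | 20.0% | 18.4% | 15.8% | 11.1% |
| 30% | 30.0% | 27.8% | 24.3% | 17.6% |

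Across these rows, the relative understatement is about 19–23% at r = 0.75 and 41–47% at r = 0.5.

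**Against sampling error.** With the target of 240 enrollees per site (2.2, 6.3) and p = 20%, the exact binomial 95% interval at r = 0.5 is about 7.5–15.9%, which excludes 20%. At r = 0.75 it is 11.5–21.1%, which still contains 20%.

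**The case against.** A reader might infer that the plan cannot estimate prevalence at all, or that it returns a value near zero by construction. That would follow if only status at the moment of enrollment counted: 0 of 240 has an upper 95% limit of 1.5%. The endpoint definition does not say this. It includes findings at screening, and treated women may enroll.

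Four further points favor the plan:
- Selective loss is plausible but not shown. With r = 1 there is no bias. STD treatment is free (2.2, 7.4), symptoms can be treated at the Screening Visit (4.2.2), and repeat screening is allowed (3.3).
- Section 3 states that the eligibility criteria are consistent with HPTN 035. The objectives use the same target-population phrase for seroincidence and retention, which can be measured only in enrollees. Enrollees with their pre-treatment results are therefore a defensible population.
- A reader might also infer that screening losses go unseen. They do not: the screening outcome of each screenee is an endpoint, and 6.4.2 tabulates reasons for ineligibility.
- Not every listed condition is affected alike. Asymptomatic candidiasis does not block enrollment, and other genital signs and symptoms are not in themselves an exclusion.

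All four stand and limit the claim. They do not settle which result counts. Nor does a table of ineligibility reasons replace a prevalence estimate, since it need not identify infected women who simply did not return.

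**Conclusion.** The concern holds in a limited form. The enrollee-only formula conditions on a step that depends on the outcome, and it understates prevalence among otherwise eligible screened women whenever r is below 1. The size ranges from nothing at r = 1 to a drop from 20.0% to 11.1% at r = 0.5, on an assumed true prevalence of 20%. The documents do not allow r to be fixed, so no single figure should be quoted as the bias. The calculation assumes that pre-treatment results are used, which 6.4.2 should state.

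This affects a descriptive secondary objective. The primary HIV seroincidence estimate is untouched.

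**What to change.** In 6.4.2:
1. State that the first pre-treatment result counts, whether from screening or from the first Enrollment Visit exam, and that this also holds when screening is repeated.
2. Add prevalence of chlamydia, gonorrhea and syphilis among all HIV-uninfected women with a screening result.
3. Add prevalence of pelvic-exam and wet-mount conditions among all women examined at their first Enrollment Visit exam, whether or not they enrolled.
4. Give exact binomial 95% intervals for these figures.
5. Keep the enrollee-only figure, labeled as a description of the cohort.

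No new tests or visits are needed. The cost is some extra analysis and keeping the results of women who were screened but not enrolled.

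Two limits should be reported with the figures. Screening stops once ineligibility is known (4.2, 4.3), and the pelvic exam is done only in women who return and test negative for pregnancy (3.3). The exam-based figure therefore still omits women who never returned or were not examined. Also, women treated for symptoms at the Screening Visit may already have been treated when first examined.
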